13.4.2. Reporting Adverse Events to the Responsible IEC/IRB and Health Authorities

Adverse events that meet the IEC/IRB requirements for reporting must be reported within the IEC/IRB's written guidelines. Each clinical site will refer to and follow any guidelines set forth by their Approving IEC/IRB. Each clinical site will refer to and follow any guidelines set forth by their local governing Health Authorities.

The Sponsor will report applicable Adverse Events to the local health authorities according to the written guidelines, including reporting timelines.

13.5. Event of Special Interest

None

13.6. Reporting of Pregnancy

Subjects reporting pregnancy (by self-report) during the study will be discontinued after the event is recorded as an Adverse Event. Once discontinued, pregnant participants and their fetuses will not be monitored for study related purposes. Pregnant participants are not discontinued from contact lens or solution related studies for safety concerns, but due to general concerns relating to pregnancy and contact lens use. Specifically, pregnant women are discontinued due to fluctuations in refractive error and/or visual acuity that occur secondary to systemic hormonal changes, and not due to unforeseen health risks to the mother or fetus.

14. STATISTICAL METHODS

14.1. General Considerations

Statistical Analysis will be undertaken by the sponsor or under the authority of the sponsor. A general description of the statistical methods to be implemented in this clinical trial is outlined below. More details will be included in the stand-alone Statistical Analysis Plan (SAP). The SAP will be developed and finalized prior to database lock.

All data summaries and statistical analyses will be performed using the Statistical Analysis System (SAS) software Version 9.4 or higher (SAS Institute, Cary, NC).¹⁵ Throughout the analysis of data, the results for each subject/eye will be used when available for summarization and statistical analysis. Unscheduled visits will be summarized separately and will be excluded from the statistical analysis.

Summary tables (Descriptive statistics and/or frequency tables) will be provided for all baseline variables, efficacy variables and safety variables as appropriate. Continuous variables will be summarized with descriptive statistics (n, mean, standard deviation [SD], median, minimum and maximum). Frequency count and percentage of subjects or eyes within each category will be provided for categorical data.

Summaries will be presented by separately for each lens type (Test and Control) and time point (baseline, fitting, 3-Day follow-up, 1-week follow-up, exit evaluation and unscheduled visits

(when applicable)) and will be performed separately by completion status (Safety Population, Per-Protocol Population and Intent-to-Treat, when appropriate).

14.2. Sample Size Justification

This study was designed and powered to test for superiority of the Test lens relative to the DT1MF lens after 1-week of optimized lens wear with respect to clarity of vision in dim or low lighting and clarity of vision when reading in dim light. Additionally, this study was also powered to test the following after 1-week of optimized lens wear: superiority of the Test lens compared to DT1MF with respect to clarity of intermediate and near vision as well as non-inferiority with respect to clarity of distance vision.

The sample size for co-primary endpoints was estimated to achieve a minimum statistical power of 90% using a 2-sided type I error rate of 5% each and a minimum statistical power of 90% for the secondary endpoints using a 2-sided type I error rate of 1.67% each (5% familywise error rate).

Historical data from two study was utilized in the sample size calculation for this study. Both clinical studies, were 2x3 crossover designs with 1-week follow-up evaluation for the optimized lens wear. Table 6 below summaries the historical studies and Table 7 displays the estimated odds ratio and corresponding 95% CIs.

Table 6: Summary of Historical Studies Included in Sample Size Calculations

Study Number	Population	Design	Number Enrolled	Number Completed	Number included in PP population	Number in ITT population
Tuilibei		- 0				population
	Hyperopes	2x3	78	75	64	75
	Myopes	2x3	81	78	66	78

PP: Per-Protocol; ITT: Intent-to-treat

Table 7: Historical Odds Ratio Estimates and 95% CIs – Intent-to-Treat Population

		Estimated Odds	95% Confidence
Endpoint Type	Item	Ratio	Interval
Primary	Clarity of vision in low	1.67	(1.10, 2.53)
	lighting conditions		
	Clarity of vision when	1.88	(1.26, 2.82)
	reading in low light		
Secondary	Clarity of distance vision	1.27	(0.82, 1.98)
	Clarity of intermediate	1.98	(1.25, 3.13)
	vision		
	Clarity of near vision	2.28	(1.49, 3.48)

Odds ratios were calculated as Test over DT1MF

Odds ratio represents odds of having a more positive experience while wearing the Test lens compared to DT1MF

Primary and Secondary Sample Size Estimates

Sample size estimates for each co-primary and secondary endpoint were carried out separately using an approximation of the power of an F-test derived from the non-centrality parameter calculated from the observed F statistic of a linear model. Each endpoint was analyzed individually using a generalized linear mixed model with a multinomial distribution and the cumulative logit as the link function. Sequence of lens wear, period, lens and first order carryover effect were included in the model as fixed effects. Study nested within site was included as a random effect (G-side). Errors between measurements within the same subject across periods was model using a variance component (VC) covariance structure. The Kenward and Roger method was used for the calculation of the denominator degrees of freedom.¹⁶

To estimate the sample size for each co-primary and secondary endpoints, the odds ratio and the cumulative log-odds from the model described above for each endpoint was used to create a new dataset with the same structure and design as the historical studies. This new dataset was then analyzed using a generalized linear model with a multinomial distribution and the cumulative logit as the link function. Lens type was included as the only fixed effect; errors between measurements within the same subject across periods was model using a variance component (VC) covariance structure. The Kenward and Roger method was used for the calculation of the denominator degrees of freedom. The statistical power of each endpoint was calculated using the F-statistics as Power=P(F[Fcrit, v, ncp] > Fcrit); where Fcrit is the critical value of the central F distribution (Fcrit= $F_{[numdf,dmdf,0,alpha]}$) under Ho (Ho: centrality param = 0), v is the magnitude of the departure from Ho and ncp is the non-centrality parameter (Stroup).¹⁷

Table 8 displays the sample size estimates and associated power by endpoint. As indicated below, co-primary endpoints were powered \sim 92% individually yielding a combined power of \sim 85%. With respect to secondary endpoints, each hypothesis was also powered to at least \sim 96% power provided a combine power of \sim 93%. Therefore, the overall combined study power for co-primary and secondary hypotheses is 79.2% and is considered reasonable to support any conclusions from these analyses.

Table 8: Sample Size Estimates by Endpoint

Endpoint			# of Subjects	
Type	Item	Alpha	Complete	Power (%)
Primary	Clarity of vision in low lighting conditions	0.05	110	92
	Clarity of vision when reading in low light	0.05	69	92
Secondary	Clarity of distance vision (non-inferiority)	0.0167	83	99
	Clarity of intermediate vision	0.0167	110	98

Endpoint			# of Subjects	
Type	Item	Alpha	Complete	Power (%)
	Clarity of near vision	0.0167	110	96

Based on the table above a total of at least 110 subjects are required to complete the study. To account for screen failures and subject dropout up to 130 hyperopic and myopic subjects will be targeted to be enrolled in this study to the aim of 110 (N=66, myopes and N=44 hyperopes) to complete. The allocation of 1:1.5 (hyperopes: myopes) was chosen based on the market representation and availability of subject population.

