4.2. Study Design Rationale

Crossover designs are a well-established study design in which subjects are exposed to multiple treatments during different time periods. A 2×3 bilateral crossover design was considered to be the optimal design since the study period is relatively short, the design can be cost effective, and more efficient comparisons between treatments can be made. As compared to a parallel study since fewer subjects are required to achieve the same pre-specified statistical power. Each subject will act as their own control to reduce the influence of potential confounding factors such as age, gender and vision correction.

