14.5. Primary Analysis

The primary analyses will be conducted on the intent-to-treat population.

Clarity of Vision in Dim or Low Lighting and Clarity of Vision when Reading in Dim light Subjective responses for co-primary endpoint will be the outcome (*aval*) defined as category one if a subject responds' 'Excellent' or 'Very Good', the outcome is defined as category two

if a subject responds' 'Good' and the outcome is defined as category three if a subject responds' 'Fair' or 'Poor'.

Since both co-primary endpoints assess various aspects of vision in dim or low light, the association between the two endpoints will be assessed using a Cochran-Mantel-Haenszel chi-square test using the Frequency PROCEDURE in SAS 9.4. If the association between the co-primary endpoints is statistically significant at an alpha=0.05 then the following analysis methods will be implemented:

Primary Analysis Plan A (If associate between co-primary endpoints is significant)

The outcomes for co-primary endpoints will be analyzed together using a hierarchical generalized linear mixed model (GLMM) with a multinomial distribution and the cumulative logit as the link function. Sequence of lens wear, period, lens type, first order carryover effect, item and the interaction between lens by item will be included as fixed effects. Site and subject nested within site will be included as random effects. Residual errors between measurements within the same subject and period across items will be modeled using an unstructured covariance (UN) structure. If this structure fails to converge then a variance component (VC) structure will be used. The Kenward and Roger method will be used for the calculation of the denominator degrees of freedom.¹⁶

Comparisons between the Test and DT1MF will be carried separately for each item out using 2-sided 95% confidence intervals (CIs) constructed for the odds ratio (Test over DT1MF). Superiority will be concluded if a lower limit of a 95% CI is above 1.

The Model:

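### Four of the five powers in Table 8, and the 90% minimum power statement, do not follow from Table 7 or from the power method described

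*Combined protocol and SAP*

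**What the plan says.** Section 14.2 describes the sample size in three steps.

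- **Source of the effects.** "Historical data from two study was utilized in the sample size calculation for this study". Both studies were 2x3 crossovers. Table 6 gives 75 and 78 intent-to-treat subjects, and Table 7 gives odds ratios (Test over control) with 95% confidence intervals for that population.
- **Method.** Each endpoint was first fitted with a cumulative-logit mixed model. Then "the odds ratio and the cumulative log-odds from the model described above for each endpoint was used to create a new dataset", which was analysed with a reduced model: "Lens type was included as the only fixed effect; errors between measurements within the same subject across periods was model using a variance component" (VC) structure. Power came from a non-central F distribution.
- **Result.** For the co-primaries the sample size "was estimated to achieve a minimum statistical power of 90% using a 2-sided type I error rate of 5% each". The secondaries have the same 90% target at 1.67% each. Table 8 lists the power per endpoint, and the text concludes: "Based on the table above a total of at least 110 subjects are required to complete the study". It adds that "the overall combined study power for co-primary and secondary hypotheses is 79.2% and is considered reasonable to support any conclusions from these analyses".

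Section 4.2 justifies the crossover partly because "Each subject will act as their own control". In Section 14.5, Plan A states: "Site and subject nested within site will be included as random effects". Plan B uses an unstructured within-subject covariance. Section 2.3 requires every co-primary and secondary hypothesis to succeed for the study objective to be satisfied.

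**The concern.** Table 7 shows how precisely 153 subjects in this design estimated each lens effect. For low light, the lower limit of 1.10 is not far above 1, and the estimate is only about 2.4 standard errors from no effect. It is hard to see how 110 subjects would then detect the same effect 92% of the time. Distance, intermediate and reading raise the same question.

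There is also an ordering problem. Near has a larger odds ratio than intermediate (2.28 against 1.98) and a smaller standard error, at the same N and alpha, yet its stated power is lower (96% against 98%). That needs an explanation, though it does not prove an error.

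The target of 110 completers rests on this table. If its powers are overstated, the chance of meeting all five hypotheses is well below what readers of the plan are told.

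**Working it through.** **The plan's own combined figures.** From Table 8, 0.92 × 0.92 = 84.6% (stated about 85%), 0.99 × 0.98 × 0.96 = 93.1% (stated about 93%), and the product of all five is 78.8% (stated 79.2%; 0.85 × 0.93 = 79.05%). These follow from Table 8 within rounding, so they stand or fall with it.

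**Check 1: Table 7 scaled to Table 8's Ns.** Inputs are the odds ratios and limits in Table 7, 75 + 78 = 153 subjects from Table 6, Ns and alphas from Table 8, and the 0.67 margin from Section 14.6.

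- SE = (ln U − ln L)/3.92
- z at 153 = ln(OR)/SE; for distance, ln(1.27/0.67)/SE
- Power = Φ(z × √(N/153) − z_crit), with z_crit = 1.960 (5%) or 2.394 (1.67%)

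For low light, SE = ln(2.53/1.10)/3.92 = 0.2125 and z = 0.5128/0.2125 = 2.41. At N=110, z = 2.41 × √(110/153) = 2.05, and power = Φ(2.05 − 1.96) = 53%.

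| Endpoint | SE | z at 153 | N | Power from Table 7 | Stated | Power at N=153 |
|---|---|---|---|---|---|---|
| Low light | 0.2125 | 2.41 | 110 | 53% | 92% | 67% |
| Reading | 0.2055 | 3.07 | 69 | 54% | 92% | 87% |
| Distance (NI) | 0.2249 | 2.84 | 83 | 38% | 99% | 67% |
| Intermediate | 0.2342 | 2.92 | 110 | 53% | 98% | 70% |
| Near | 0.2164 | 3.81 | 110 | 80% | 96% | 92% |

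The last column needs no scaling: even the whole historical sample falls short of every stated power. Moving all odds ratios and limits by ±0.005 changes the scaled powers by little more than one point. With all five endpoints at N=110 the results are 53/74/51/53/80%. Distance is analysed per protocol; if the historical fraction of 130/153 holds, about 93 of 110 remain and distance has 43%.

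The information per subject needed to reach the stated powers, relative to Table 7, is (z needed / z at Table 8 N)². With z needed of 3.37, 3.37, 4.72, 4.45 and 4.14, the ratios are 2.7, 2.7, 5.1, 3.2 and 1.7.

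**Check 2: the stated method.** The plan does not say whether VC means independent errors or a subject variance component, so both readings were tried.

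*(a) Independent errors.* The Fisher information for the lens effect in a cumulative-logit model with 3N observations was maximised over all response distributions, because the cumulative log-odds are not printed. Power is from the non-central F with 1 and 3N − 2 degrees of freedom.

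| | Low light | Reading | Distance | Intermediate | Near |
|---|---|---|---|---|---|
| Ceiling, 3 categories | 71% | 68% | 63% | 82% | 94% |
| Ceiling, 5 categories | 74% | 71% | 67% | 85% | 96% |
| Stated | 92% | 92% | 99% | 98% | 96% |

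These are upper limits, so no choice of cumulative log-odds closes the first four gaps. Near is attainable in the best case, which is why the count is four of five.

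*(b) Subject variance component.* The historical model used the same VC structure, so on this reading Table 7 already contains it. What remains is the gain from dropping sequence, period and carryover. In a linear-model approximation for this design the lens variance is 0.750(1 − ρ) with those terms, against 0.667 lens-only at ρ = 0. The gain in information is at most 0.750/0.667 = 1.125, and it is smaller at higher ρ. Multiplying the Check 1 information by 1.125 gives 58/59/43/59/85%.

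One-sided alpha, alpha 0.05 for the secondaries, the per-protocol 130 as the base, and N read as per sequence were also tried. None brought any of the first four rows within two points of its stated power.

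**The case against.** The strongest reply is that within-subject correlation is missing from these checks. If Table 7 comes from a model with independent errors, its intervals ignore pairing, and the planned analysis would be more precise. On the most favourable three-category split, with information scaled by 1/(1 − ρ), the correlations needed to match Table 8 are about 0.44 (low light), 0.47 (reading) and 0.44 (intermediate). One unprinted value a little under 0.5 would therefore account for three of the four rows. The cumulative log-odds and variance components are not printed either, so the sponsor's run cannot be repeated exactly, and Section 14.1 defers detail to a stand-alone SAP.

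Part of this stands: the 53/54/38/53/80% figures are not the trial's true power. But the plan documents no correlation and does not say one was carried into the power dataset. The same reckoning needs about 0.66 for distance and 0.07 for near, so no single value fits the table.

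Two smaller points are fair. The divisor 3.92 assumes large degrees of freedom, whereas the plan used Kenward-Roger degrees of freedom that are not reported. With 20 the Table 7 route gives 59/59/43/59/85%, and with 10 it gives 64/65/50/66/90%, still short. The distance figures also apply an intent-to-treat odds ratio and SE to a per-protocol analysis, because no per-protocol estimate is printed.

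Finally, the joint power multiplies values quoted at N = 69, 83 and 110 as if the endpoints were independent. Given Table 8, both features would tend to understate joint power if endpoints are positively associated and 110 subjects complete. The joint figure's real weakness is that it inherits Table 8.

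**Conclusion.** The concern holds. The stated powers for low light, reading, distance and intermediate, and the 90% minimum, are not supported by Table 7 or by the method in Section 14.2 on either reading of VC. The shortfall is 38 to 61 percentage points on the Table 7 route and 16 to 36 points against the most generous three-category ceiling. Near is below its stated value on Table 7 (80% against 96%) but attainable under the method's best case.

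This rests on Table 7 being the planning input, as the plan says, on precision scaling with the number of subjects, and on large degrees of freedom. It does not establish what the true power is. As illustration only, treating Table 7 as the no-correlation case and replacing n by n/(1 − ρ), with N=110 and about 93 for distance, ρ = 0.3 gives 69/88/60/71/93% and ρ = 0.5 gives 82/96/77/86/98%. The answer depends heavily on a quantity the plan does not state.

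This must be corrected because Table 8 is the justification for 110 completers. The confidence-interval decision rules and type I error control are untouched.

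**What to change.** - Recompute power for each endpoint under the final analysis model (sequence, period, lens, carryover and within-subject covariance) at 110 completers. For distance use the expected per-protocol number, about 93 if the historical fraction holds.
- Take the covariance and cumulative log-odds from the historical data. Print them with the non-centrality parameters, and state what VC means.
- Replace the Table 8 powers, the approximate 85% and 93%, the 79.2% and the 90% minimum with the results. State the between-endpoint assumption behind any joint power. If near still ranks below intermediate, explain why.
- If no correlation can be justified, show power over a range of ρ, with the Table 7-scaled figures as the no-correlation case.

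The cost is a recalculation from data the sponsor already holds, plus a revision of Section 14.2 and the SAP. The restated power may be less favourable. No added enrolment is requested.

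### The combined powers in Section 14.2 (about 85% co-primary, 79.2% overall) multiply endpoint powers taken at different numbers of completers, so they understate the power of the 110-completer trial on the plan's own inputs

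*Combined protocol and SAP*

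**What the plan says.** Section 14.2 targets, for the co-primary endpoints, a "minimum statistical power of 90% using a 2-sided type I error rate of 5% each", and the same 90% floor at 1.67% each for the secondary endpoints. Table 8 then gives alpha, number of subjects completing and power (%) for each endpoint:

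- "Clarity of vision in low lighting conditions 0.05 110 92"
- "Clarity of vision when reading in low light 0.05 69 92"
- "Clarity of distance vision (non-inferiority) 0.0167 83 99"
- "Clarity of intermediate vision 0.0167 110 98"
- "Clarity of near vision 0.0167 110 96"

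The text introducing the table reports a combined power of about 85% for the co-primary pair and about 93% for the three secondary tests, and concludes that "the overall combined study power for co-primary and secondary hypotheses is 79.2% and is considered reasonable to support any conclusions from these analyses". After the table the trial receives one size: "Based on the table above a total of at least 110 subjects are required to complete the study".

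Three other places bear on this. Section 2.3 makes the study objective depend on all five hypotheses being met. Section 14.6 analyses distance vision per-protocol, while the other four tests are intent-to-treat. Section 14.5 plans a test of association between the two low-light items and provides one analysis for each outcome of that test.

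**The concern.** A product of powers describes a trial only if every factor is the power of a test in that trial. Here one co-primary factor is a power at 69 completers and the other a power at 110, and the overall product adds a third size, 83. No trial has 69 completers for one questionnaire item and 110 for another item on the same questionnaire.

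What is at stake is the accuracy of a stated operating characteristic. Because all five tests must succeed, 79.2% is the plan's only figure for the chance of meeting its objective, and the plan judges the design reasonable on it.

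**Working it through.** **Inputs.** The alpha, number of completers and power of each Table 8 row; 110 planned completers (Section 14.2); per-protocol and ITT counts in the two historical studies (Table 6).

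**Step 1: reproduce the stated figures.**

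- Co-primary: 0.92 × 0.92 = 0.846, stated as about 85%.
- Secondary: 0.99 × 0.98 × 0.96 = 0.9314, stated as about 93%.
- Overall: 0.85 × 0.9314 = 0.792, the stated 79.2%. With 0.846 unrounded the product is 0.788.

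So the overall figure is the product of powers at 110, 69, 83, 110 and 110 completers.

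**Step 2: move the two odd rows to the trial's size.** The plan's method works from a non-centrality parameter. I assume that this is proportional to the number of subjects. On the normal scale, power at N₂ is Φ[(z₁₋α/₂ + z_power) × √(N₂/N₁) − z₁₋α/₂].

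- Reading, 69 to 110: (1.960 + 1.405) × √(110/69) = 4.249; Φ(4.249 − 1.960) = Φ(2.289) = 0.989.
- Distance, 83 to 110: (2.393 + 2.326) × √(110/83) = 5.433; Φ(3.040) = 0.999.
- Distance at an assumed per-protocol number: Table 6 has 64 + 66 = 130 per-protocol of 75 + 78 = 153 ITT subjects, so 110 × 130/153 = 93.5; 4.719 × √(93.5/83) = 5.009; Φ(2.616) = 0.996.

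The other three rows are already at 110. For the ITT tests I take 110 analysable subjects, because ITT and completer counts coincided in both historical studies. This too is an assumption.

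**Step 3: recombine with the plan's own product rule.** Co-primary: 0.92 × 0.989 = 0.910.

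| Distance counted at | Distance power | Secondary product | All five |
|---|---|---|---|
| 83 | 0.990 | 0.931 | 0.847 |
| 93.5 | 0.996 | 0.937 | 0.852 |
| 110 | 0.999 | 0.940 | 0.855 |
| Stated | 0.990 | about 0.93 | 0.792 |

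Correcting the reading row alone takes the unrounded product from 78.8% to 84.7%. Distance adds at most a further 0.8 points (85.5 − 84.7).

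**Step 4: sensitivity.** With distance at 110, a non-central F with denominator degrees of freedom n − 1, 2n or 3n − 2 gives 85.5% to 85.6% overall. Shifting all Table 8 powers down or up by their rounding error gives 84.0% to 87.0%.

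**Step 5: dependence.** The product assumes independent tests, although all five come from the same subjects. At 110, and at the printed powers, the co-primary joint power lies between 0.920 + 0.989 − 1 = 0.909 and 0.920 under any dependence. For all five, with distance left at 83, the floor is 1 − (0.080 + 0.011 + 0.010 + 0.020 + 0.040) = 0.839 and the ceiling is 0.920. Positive correlation moves the joint power above the independence product.

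**Step 6: is 69 really the size behind the 92%?** Table 7 suggests so. Scale its intervals from 153 subjects, with SE = ln(upper/lower)/(2 × 1.960). Low lighting has SE 0.2125 and gives 53.4% at 110. Reading has SE 0.2055 and gives 54.1% at 69 but 74.0% at 110. The two items match, as they do in Table 8, only when reading is taken at 69.

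**The case against.** The strongest reply is that nothing turns on this. Power at 110 is at least the listed power in every row, positive correlation adds to it, and the 110 is fixed by the low-lighting row, which does not change. On the plan's inputs 79% is therefore a safe understatement, and a design judged reasonable at 79% is more so at 85%. That stands and sets the severity. It does not make the figure right: the plan presents 79.2% as the study's power, not as a lower bound.

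A second reply is that 83 may be a deliberate allowance for per-protocol exclusions. The documents do not say, and 83 cannot be called wrong. Leaving it untouched still gives 84.7%, so the point does not depend on it.

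Two further readings are tempting and not supported. A reader might infer from 79.2% against 78.8% that the authors rounded too early. Whole-percent entries cannot show this: 0.922 × 0.922 = 0.850, which prints as 92% twice and also leads to 79.2%. A reader might also infer that the plan itself expects the two low-light items to be associated. Section 14.5 only tests for association and keeps a full alternative analysis if none is found. The case against treating the product as exact rests on the shared subjects.

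**Conclusion.** The point holds as a minor restatement. On the plan's own inputs at 110 completers, the co-primary combined power is about 91% rather than about 85%, and the overall figure about 85% rather than 79.2%. The secondary figure stays at 93% to 94%. The gaps of about six points come almost entirely from the reading item. They rest on three assumptions: Table 8 at face value, non-centrality proportional to the number of subjects, and 110 analysable ITT subjects.

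A reader might infer that the trial is too small. The documents do not support that from this error, which runs in the conservative direction. A reader might equally take 85% as reassurance. That is not supported either: the recalculation inherits the individual Table 8 powers without testing them. The Table 7 intervals, which come from a model with carryover, imply much lower absolute powers (Step 6) than Table 8, which used a model with lens type only. Whether the Table 8 entries are right is a separate question; whatever the answer, they must be combined at one trial size.

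**What to change.** In Section 14.2, recompute the reading row of Table 8 at 110 completers and the distance row at a stated expected per-protocol number, giving its basis. Restate the 85%, 93% and 79.2% figures at that single trial size. Then either say that the product assumes independent tests, or replace it with a joint power for all five tests simulated under the planned model and alpha levels. The simulation needs between-item correlations. The documents do not report these, so they would have to come from the sponsor's historical data.

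The cost is one rerun of the planning calculation and a few restated figures. The simulation is optional extra work. Sample size, alpha levels and analyses do not change.
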